4.6.5. Additional Efficacy Analyses

4.6.5.1. Clinically meaningful reduction at Month 3 for the two co-primary endpoints with

Sponsor:	ObsEva		
Protocol:	18-OBE2109-003		
Document Version No.:	V5.0	Document Date:	13-JUN-2022

discontinued subjects considered as non-responders

A supportive analysis of the co-primary endpoint analysis will be conducted that considers all subjects who prematurely discontinue the study treatment before the Month 3 visit as non-responders. These are composite endpoints that estimate the proportion of subjects with clinically meaningful reduction in pain, a stable or decreased use of rescue medication, and who complete 3 months of treatment. The same analyses as described in Section 4.6.2.1.2 will be performed, i.e., using a composite strategy for discontinuation as opposed to a while on treatment strategy used for the primary estimand.

The analysis will be performed on the Full Analysis Set and the Per Protocol Set.

4.6.5.2. Clinically meaningful reduction at Month 3 for the two co-primary endpoints with multiple imputation approach for subjects who discontinued the study early

As supportive analysis of the co-primary endpoint analysis, in order to estimate the effect of treatment policy, a reference based multiple imputation approach will be used for the co-primary endpoints for subjects who discontinue the study early, under the assumption that the efficacy of the linzagolix treated subjects gradually transitions to that observed in the placebo subjects, i.e., using a treatment policy strategy for discontinuation as opposed to a while on treatment strategy used for the primary estimand.

Details on multiple imputation methodology are described in section 4.2.8.

DYS and NMPP mean scores changes, and ibuprofen and analgesic use (pill counts) will be simultaneously imputed using multivariate imputation by a fully conditional specification method, with 20 burn-in iterations before each imputation. The predictive mean matching method for continuous variables will be used where the imputed values will be randomly taken from the 5 closest observed values whose predicted values are closest to the predicted value for the missing value from the simulated imputation model. The imputation model will include baseline value as a covariate. Following imputation, the corresponding binary endpoints of response for DYS, NMPP including use of analgesics, will be computed.

For each imputed dataset, the logistic regression analyses for DYS and NMPP as described in section 4.6.2.1.2 will be performed. The combined estimate of odds ratios will be obtained from each of the m models estimates.

SAS Code for multiple imputation:

```
Step 1: Multiple imputation
    proc mi data=dataset seed=1910 nimpute=500 out=outmi;
        class treatment;
        fcs regpmm ( DYS_chg = DYS_base / k=5 ) nbiter=20;
        fcs regpmm ( ibu = ibu_base / k=5 ) nbiter=20;
        fcs regpmm ( narco = narco_base / k=5 ) nbiter=20;
        mnar model( DYS_chg / modelobs=(treatment='placebo') );
        mnar model( ibu / modelobs=(treatment='placebo') );
        mnar model( narco / modelobs=(treatment='placebo') );
```

CRS-BS-TP-000005 V 1.0

Page 85 of 127

Cytel Confidential: This is a controlled document and shall not be changed, saved, copied or reproduced by any unauthorized

Sponsor:	ObsEva		
Protocol:	18-OBE2109-003		
Document Version No.:	V5.0	Document Date:	13-JUN-2022

```
var DYS base ibu base nar base DYS chg ibu narco;
       run;
      data outmi2 ;
          set outmi ;
          /* Derive binary endpoints as described in primary endpoint section*/
      Run;
 Step 2: Statistical analysis for treatment effect: Logistic Regression
      PROC LOGISTIC data=outmi2 order=internal;
             By _imputation_ ;
             Class treatment (ref=placebo);
             Model DYS resp(event= "Yes") = treatment DYS base /alpha=0.05;
             Oddsratio treatment ;
             Lsmeans treatment / ilink exp cl alpha=0.05 at means diffs=control("1")
             adjust=bon;
             Ods output OddsRatiosWald=or
             lsmeans=lsm diffs=diffs ParameterEstimates=es;
      run;
 Step 3: Combine estimates from each imputation dataset
 Data or2 ;
      Set diffs ;
      Logodds=estimate;
      Logoddsse=(AdjUpper-AdjLower)/(2*2.24);
 Run;
 proc mianalyze data=or2;
   ods output parameterestimates=mian_logodds;
   modeleffects logodds;
   stderr logoddsse;
 run;
* Back-transform to get odds ratio ;
 data mian odds; set mian logodds;
   estimate_back = exp(estimate); *pooled odds ratio;
   lcl_back=estimate_back*exp(-2.24*stderr); *pooled lower limit;
   ucl back=estimate back*exp(+2.24*stderr); *pooled upper limit;
 run;
* pooled p-value ;
      %macro trtby(n=);
      data es_;
        set es;
        where variable in ('treatment') and CLASSVALO="&n";
      run;
      proc sort data=es out=lgs anoval es;
        by variable imputation ;
      run;
      ** calculate Rx;
      data lgs_anova2_es;
```

CRS-BS-TP-000005 V 1.0

Page 86 of 127

Cytel Confidential: This is a controlled document and shall not be changed, saved, copied or reproduced by any unauthorized

Sponsor:	ObsEva		
Protocol:	18-OBE2109-003		
Document Version No.:	V5.0	Document Date:	13-JUN-2022

```
set lqs anoval es;
        by variable imputation ;
        StChi=SQRT(WaldChiSq);
      run;
      proc means data=lgs anova2 es noprint;
        by variable ;
        var StChi;
        output out=lgs anova3 es(drop= :) mean=mnStChi;
       run;
      data lgs anova4 es;
        merge lgs anova2 es lgs anova3 es;
        by variable ;
        StDif2=(StChi-mnStChi) **2;
      run;
      proc means data=lgs anova4 es noprint;
        by variable ;
        var df WaldChiSq StDif2;
        output out=lgs anova5 es(drop= t: rename=( freq =M)) mean=DF mnChi2 mnStDif2
sum=smDf smChi2 smStDif2;
      run;
      data lgs anova6 es &n;
        set lgs anova5 es;
        by variable ;
        Rx=(1+1/M) / (M-1) *smStDif2;
        Dx=(mnChi2/DF-(M+1)/(M-1)*Rx)/(1+Rx);
        DF d=DF**(-3/M)*(M-1)*(1+1/Rx)**2;
        Pval=1-CDF("F", Dx, DF, DF d);
        trtn=&n;
       run;
%mend;
%trtby(n=2);
%trtby(n=3);
/* Bonferroni adjustment */
      data bonf_2 ;
             set LGS ANOVA6 ES 2 ;
             pvalbon=pval * 2 ;
             if pvalbon > 1 then pvalbon = 1;
      run;
```

SAS Code may be updated to fit the data.

The analysis will be performed on the Full Analysis Set.

4.6.5.3. Clinically meaningful reduction at Month 3 for the two co-primary endpoints with stable or decreased use of analgesics for EAP assessed across all days

An additional analysis of DYS and of NMPP will be conducted where the assessment of stable or decreased use of analgesics for EAP will be assessed over all days rather than separately for bleeding days

Sponsor:	ObsEva		
Protocol:	18-OBE2109-003		
Document Version No.:	V5.0	Document Date:	13-JUN-2022

and non-bleeding days. This same assessment will then be incorporated into the DYS and NMPP endpoints. The same logistic regression analysis as described at the start of Section 4.6.2.1.2 will be performed.

The analysis will be performed on the Full Analysis Set.

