4.6.2.1.2. Primary Efficacy Analysis

The primary efficacy analysis will be conducted using the FAS.

The analysis of each co-primary endpoint will be conducted using a logistic regression model, with treatment group as the main effect (three values) and including the baseline pain score as a covariate. Individual linzagolix versus placebo treatment group comparisons will be made using the same logistic regression model. Estimated odds-ratios and 97.5% intervals of proportions of responders of linzagolix treatment groups versus placebo will be presented, along with Bonferroni corrected p-values. Estimates of proportions of responders with 95% confidence intervals will be presented as well, estimated at the overall mean baseline pain score.

SAS Code (may be updated at analysis stage to fit the data):

```
PROC LOGISTIC data=dataset order=internal;
Class treatment(ref=placebo) / param=glm ;
Model resp(event= "Yes")= treatment base_pain /alpha=0.05;
Oddsratio treatment ;
Lsmeans treatment / ilink exp cl alpha=0.05 at means diffs=control('1')
adjust=bon;
Ods output OddsRatiosWald=or ModelANOVA=ma ParameterEstimates=pe
lsmeans=lsm diffs=diffs;
```

Run;

In addition, the mean pelvic pain scores for DYS and NMPP and change from baseline for the last 28 days prior to Month 3 or the last 28 days of treatment (or less) for subjects who discontinued will be summarized as continuous variables by treatment group. Cumulative distribution functions (CDF) for change from baseline at Month 3 for DYS and NMPP will be provided, with separate lines for each treatment group. The x-axis will present the different values for the DYS or NMPP change from baseline, and the y-axis will present the proportion of subjects reaching each value of change. Vertical lines of the relevant MCT thresholds obtained at the Month 3 responder threshold analysis will be displayed on the plots.

The number and percentage of subjects with:

- Reduction of X for DYS,
- Reduction of X for NMPP,

Sponsor:	ObsEva		
Protocol:	18-OBE2109-003		
Document Version No.:	V5.0 Document Date: 13-JUN-2022		

- Stable or decreased use of analgesics for EAP during bleeding days, during non-bleeding days, and overall,
- Reduction of X for DYS and stable or decreased use of analgesics for EAP (during bleeding days),
- Reduction of X for NMPP and stable or decreased use of analgesics for EAP (during non-bleeding days),

will be presented.

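### SAP 4.6.5.2, Step 3: the pooling code for the supportive treatment-policy analysis has no BY for the comparison, so the two doses' odds ratios would be averaged into one

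*SAP*

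**What the plan says.** The analysis is set out in SAP 4.6.5.2 as support for the co-primary analysis. It has three coded steps.

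- **Imputation.** "proc mi data=dataset seed=1910 nimpute=500 out=outmi" creates 500 completed data sets.
- **Step 2.** A logistic model is fitted within each data set ("By _imputation"). The model is the primary one of SAP 4.6.2.1.2, "with treatment group as the main effect (three values) and including the baseline pain score as a covariate". As in the primary code, the LS-means request is "Lsmeans treatment / ilink exp cl alpha=0.05 at means diffs=control('1", that is, each active arm against control. The differences go to a data set called DIFFS.
- **Step 3.** All of DIFFS is copied to OR2. A standard error is recovered from the Bonferroni-adjusted limits ("Logoddsse=(AdjUpper-AdjLower)/(2*2.24"). PROC MIANALYZE is then called ("proc mianalyze data=or2") with a single effect, "modeleffects logodds". The result is exponentiated into one estimate and one pair of limits, for example "lcl_back=estimate_back*exp(-2.24*stderr); *pooled lower limit".

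A p-value block follows. It does not use the MIANALYZE output, and it runs once for each active arm through a macro.

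The prose is clear about what is wanted. SAP 4.2.5 tests each dose against placebo on its own, with 97.5% intervals. SAP 4.2.8.1 asks for the odds ratio of the relevant contrast, pooled on the log scale and back-transformed. SAP 4.6.2.1.2 calls for odds ratios of the linzagolix groups against placebo.

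**The concern.** With three arms and a control-difference request, DIFFS holds two rows per imputation: 75 mg against placebo and 200 mg + ABT against placebo. Nothing in Step 3 separates them. PROC MIANALYZE therefore takes every row as another imputation of the same quantity. Two things follow. The pooled log odds ratio is the plain average of the two doses. The gap between the doses is counted as between-imputation variance, so the interval widens with the difference in dose effect, which has nothing to do with missing data.

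At stake is the purpose of this analysis: to show, for each dose, whether the effect holds up when discontinuation is handled by a treatment-policy strategy instead of the while-on-treatment strategy. As coded it supplies no odds ratio for either dose, and two dose-specific p-values would stand beside one dose-averaged estimate.

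**Working it through.** **Inputs**

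- SAP 4.1: 150 per arm; DYS response 14.6% (placebo), 48.6% (75 mg), 64.7% (200 mg); NMPP response 18.8% (placebo) and 42.1% (active, used for both doses).
- SAP 4.6.5.2: 500 imputations; multiplier 2.24.
- Not in the documents: the share of variance due to imputation. It is assumed to be 0 first, then varied up to 20%.

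**The plan's own figure.** Two comparisons at an overall two-sided 0.05 give 0.025 each, so z at 0.9875 = 2.2414. The SAP's 2.24 is reproduced, and dividing the width of the adjusted interval by 2 × 2.24 recovers the ordinary standard error.

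**Correct pooling, one dose at a time (DYS, no imputation variance)**

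- Log OR, 75 mg: ln(0.486/0.514) − ln(0.146/0.854) = 1.710.
- Log OR, 200 mg + ABT: ln(0.647/0.353) − ln(0.146/0.854) = 2.372.
- Variance, 75 mg: 1/(150 × 0.146 × 0.854) + 1/(150 × 0.486 × 0.514) = 0.0535 + 0.0267 = 0.0802.
- Variance, 200 mg + ABT: 0.0535 + 1/(150 × 0.647 × 0.353) = 0.0535 + 0.0292 = 0.0827.

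**Pooling as coded (2 × 500 = 1000 rows)**

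- Mean: (1.710 + 2.372)/2 = 2.041.
- Within-imputation variance: W = (0.0802 + 0.0827)/2 = 0.0814.
- Half the gap between doses: (2.372 − 1.710)/2 = 0.331. Between-row variance: B = 0.331² × 1000/999 ≈ 0.110, all of it from the dose difference.
- Total: T = W + (1 + 1/1000)B ≈ 0.191, so SE = 0.437.
- Interval: exp(2.041 ± 2.24 × 0.437).

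| DYS | OR | 97.5% CI | SE (log scale) |
|---|---|---|---|
| 75 mg, pooled alone | 5.5 | 2.9 to 10.4 | 0.283 |
| 200 mg + ABT, pooled alone | 10.7 | 5.6 to 20.4 | 0.288 |
| As coded | 7.7 | 2.9 to 20.5 | 0.437 |

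**Sensitivity to the assumed imputation share.** From 0 to 20%, the per-dose SEs run from 0.283 to 0.317 (75 mg) and from 0.288 to 0.322 (200 mg + ABT). The coded SE runs from 0.437 to 0.460. The error stays in place throughout.

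**NMPP.** The planning rates are the same for both doses, so the gap is zero. At a 10% share, pooling by dose and pooling as coded both give OR 3.14 (1.67 to 5.89). The defect is then only that one row is reported where two are due.

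**The case against.** The strongest reply is that this is abbreviated sample code and that the prose is right. No sentence in the SAP plans a dose-averaged odds ratio. The listing carries a note that the code may be adapted to the data. It leaves the endpoint derivation as a comment, shows DYS only, and writes the Bonferroni step for one dose although the p-value macro is called for two. A programmer who has to fill one row per dose would probably see that only one row came back. SAP 4.6.5.1, which counts discontinued subjects as non-responders, gives another supportive check that is not affected.

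Much of this stands, and it limits the severity. It does not remove the error. A missing BY is wrong for any three-arm data set, so it is not a matter of fitting code to data. The p-value block of the same listing does split the arms.

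It is also true that the printed program would not reach the figures above unaided. The Step 2 CLASS statement lacks the GLM parameterization option that the primary code in 4.6.2.1.2 has, and the LS-means differences depend on it. That is a separate repair; making it leaves this error in place.

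A reader might infer that the step could hide an ineffective dose. If 75 mg had an odds ratio of 1.0 and 200 mg + ABT one of 10.7, the code would give about 3.3 (0.2 to 52, at a 10% imputation share). The arithmetic is right, but the documents do not support the scenario: their DYS planning rate for 75 mg is 48.6% against 14.6% on placebo. At the planned rates the wrongly pooled interval still excludes 1.

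**Conclusion.** Wrong as written, of minor to moderate severity. Once the class coding in Step 2 is repaired, Step 3 would return one averaged odds ratio, contrary to SAP 4.2.5, 4.2.8.1 and 4.6.2.1.2. For DYS at the planning rates the reported value, 7.7, belongs to neither dose, and its SE is about 1.5 times the correct one (0.437/0.288 = 1.52). For NMPP at the planning rates the number is practically unchanged.

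These figures rest on unadjusted Wald log odds ratios at the planning rates, without the baseline covariate, and on an assumed imputation share of 0 to 20%. The size depends on how far the doses differ.

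A reader might infer that the trial's conclusions are at risk. The documents do not support that. The analysis is supportive and gates nothing. The primary logistic model, the fixed-sequence testing and the type I error control do not use it. The dose-specific pooled p-values are computed without the MIANALYZE output, so this omission does not touch them.

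**What to change.** In SAP 4.6.5.2, Step 3:

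1. Sort OR2 by the comparison (the treatment level in DIFFS) and then by `_imputation_`.
2. Add a BY statement for the comparison to PROC MIANALYZE.
3. Carry the comparison identifier through the back-transformation.
4. Do the same for NMPP.
5. Report one pooled odds ratio with its 97.5% CI per dose, next to that dose's p-value.

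The cost is a few lines of code, with no new data and no change to the estimand. If output from this listing has already been produced, check that it was pooled by dose.

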4.6.5.4. COVID-19 Considerations

ObsEva in consultation with its Independent Data safety Monitoring Committee (IDMC) evaluated the overall benefit/risk of continuing to conduct this study during the COVID-19 pandemic and concluded that the integrity of the trial, the safety and wellbeing of trial participants and the safety of clinical trial staff were adequately assured by the measures put in place, as described below.

To ensure continuity in patient's safety monitoring, treatment, and study data collection, remote study visits, use of local laboratory and shipment of materials and study drugs from site to subject were put in place, whenever feasible, for subjects who cannot attend their visits due to quarantine, travel restrictions, site closure or other unforeseen reasons. Sites were to schedule telephone calls to subjects as replacement for on-site visits to identify adverse events and ensure continuous medical care and oversight. Phone scripts and detailed instructions for the study conduct during COVID-19 pandemic were distributed to all sites.

Any COVID-19 related study protocol deviations were being documented and regularly reviewed and analyzed by ObsEva in order to take appropriate corrective and/or preventive actions as needed.

In addition, remote monitoring visits were being approved by ObsEva when the monitors were not able to conduct in-person visits to the study sites to perform their oversight activities. The clinical monitoring plan was updated accordingly to define the content of remote monitoring visits.

ObsEva believes that COVID-19 related protocol changes do not impact the clinical data interpretability considering that:

- co-primary efficacy endpoints and most of the study secondary efficacy endpoints are patient-driven data collected by the patient on her e-diary and not during an on-site visit,
- very few protocol deviations related to COVID-19 have been reported,
- although COVID-19 could potentially affect pain values, very few participating subjects were affected with the condition, thus the impact on pain values is expected to be negligible

4.6.5.5. Daily Patient Global Impression of Severity (dPGIS), Daily Event Cancelled, Daily Difficulty

Sponsor:	ObsEva		
Protocol:	18-OBE2109-003		
Document Version No.:	V5.0	Document Date:	13-JUN-2022

Sleeping

The dPGIS, Event Cancelled and Difficulty Sleeping daily diaries were collected for subjects enrolled prior to amended Protocol V4.0 only.

The dPGIS mean scores and changes from baseline, the number of days with difficulty sleeping, the number of days for which events were cancelled and the number of days with no event planned will be computed for each 4-week period and reported in listings only.

The dPGIS scores will be calculated by averaging over the corresponding 28 calendar days immediately prior to and including the day of each scheduled assessment (or prior to and including the last dose date for subjects who discontinue treatment).

4.7. Pharmacokinetic Evaluations

Pharmacokinetic analyses will be conducted using the Pharmacokinetic Set.

PK samples are collected at each monthly visit.

For descriptive statistics of plasma concentrations mean (arithmetic and geometric), standard deviation, median, 1st and 3rd quartiles, minimum, maximum, coefficient of variation (CV%) and number of observations will be provided. Concentrations below the limit of quantification (LOQ) will be assigned a value of zero. Missing values will not be imputed, and if sufficient data are missing for a given subject, that subject may be considered non-evaluable for pharmacokinetic analysis and would not be included in the PK Set.

All plasma concentration data will be displayed in listings. PK assessment day and time, IMP intake status and IMP intake time on the day of PK assessment and on the previous days will be included in the listings.

Explorative analyses of correlations between plasma concentrations and intrinsic PK factors such as body weight/BMI, race, age will be performed, as appropriate, and will be reported separately.

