Laboratory parameters values will be summarized for each visit for each treatment group including within-group changes from baseline.

BMD values and corresponding Z-scores will be summarized at baseline and at Month 6 for each treatment group, using the observed data. The within-group percent changes from baseline for BMD values will also be summarized, including 2-sided 95% confidence intervals. Categorical summaries of percent change from baseline will also be produced. The percent changes from baseline to Month 6 will be compared between each of the linzagolix groups and the placebo group via analysis of covariance with treatment group as the main effect (three values) and including the baseline as a covariate.

Pharmacokinetic and pharmacodynamic analyses

Plasma concentrations of linzagolix and pharmacodynamic parameters, such as for example estradiol and other hormones, will be summarized by time point for each treatment group, and listed for each subject by visit day and dose regimen. Where appropriate, changes from baseline will be presented. PK/PD analyses will be reported separately.

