Document Version No.:	V5.0	Document Date:	13-JUN-2022

Pharmacokinetic (PK) Set: all subjects who received active study medication, had no major protocol deviations impacting PK evaluation and with available PK data.

In general, analyses of efficacy will be conducted using the FAS, PP and FU sets, analyses of safety will be conducted using the Safety Set and FU SAF, and analyses of PK will be conducted using the PK Set.

The actual treatment will be derived as follows, based on daily e-diary IMP intake data:

Subjects received a different kit of active linzagolix or placebo for each month, and a different kit for addback or placebo for each 3-month period.

The number of days with one pink tablet, one grey tablet and one red capsule taken based on e-diary IMP intake data for each treatment will be computed. Data from "Today" will be used primarily. If data from today is missing, data from "Yesterday" of the following day will be considered. If the e-diary is not completed for a day (neither "Today" nor "Yesterday" of following day), it will be assumed that no intake of drug was taken on that day.

Further rules are as follows:

- Treatment administration errors:
 - If a subject received placebo with placebo ABT in more than 50% of days, then the actual treatment group will be placebo with placebo ABT.
 - Otherwise, the active treatment group (combined with add-back or placebo add-back) with the most days taken will be assigned.
 - If the number of days is equal for two treatments groups containing active treatment then LGX 200 mg with ABT will be assigned.
- If a subject discontinued, only data received up to discontinuation will be used.
- It is possible that the derived actual treatment group does not correspond to any of the planned treatment groups. In that case actual treatment group will be assigned to the planned treatment group with same dose of active treatment. Example: LGX 75mg with ABT will be assigned to LGX 75mg with placebo ABT; LGX 200mg with placebo ABT will be assigned to LGX 200mg with ABT. A listing with such cases will be provided.

3.2. **Protocol Violations**

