Cytel Confidential: This is a controlled document and shall not be changed, saved, copied or reproduced by any unauthorized

Sponsor:	ObsEva		
Protocol:	18-OBE2109-003		
Document Version No.:	V5.0	Document Date:	13-JUN-2022

- At day 1: PK assessment will be included in analysis if PK sampling is done >=1.5 hours after the dose and on the same day as Day 1.
- At other visits: PK assessments will be included in analysis if:
 - Assessment is Pre-dose (or PK time = dose time), or IMP intake is not done on the day of PK sampling (i.e. considered as pre-dose), and,
 - PK assessment date is within +/-10 days of the theoretical visit and up to 2 days after last IMP intake for Month 6 visit.

If the PK sampling time is missing, or the IMP intake on the same day is done and the IMP intake time is missing then assessments will not be included.

IMP intake status (done/not done) and IMP intake time from the Pharmacokinetics eCRF page will be used.

DXA data:

Visit windows rules for DXA assessments will be the following:

- The baseline DXA assessment will be derived as the latest non-missing DXA assessment with acceptable quality (accepted="Yes") prior to the baseline visit or the first non-missing assessment with acceptable quality (accepted="Yes") done up to 10 days after the baseline visit if there is no assessment prior to baseline..
- The DXA assessment at Month 6 will be derived as the first non-missing DXA assessment with acceptable quality (accepted="Yes") and dated between Month 6 theoretical date (=Day 169) 28 days and Month 6 theoretical date + 28 days.
- The DXA assessment at Month 6 Follow-Up will be derived in the same way as the DXA assessment at Month 6. Theoretical date of Month 6 Follow-up is 168 days after Month 6 theoretical date or after treatment discontinuation.

Other Safety Data:

Endometrial biopsy Screening window will include any assessment done prior to the first dose.

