4.8.4. Laboratory Data

Clinical laboratory values will be expressed using conventional SI units.

Hematology, coagulation parameters, chemistry and lipids are assessed at screening and at each visit during the treatment period, as well as at M1 FU and M3 FU visits. E2, progesterone (P4) and LH will be assessed at each visit during the treatment period (not at the screening visit), as well as at M1 FU and M3 FU visits. Serum levels of anti-müllerian hormone (AMH) and fasting glucose will be assessed on Day 1 only. Serum levels of sex hormone-binding globulin (SHBG) will be assessed on Day 1 and Month 3 and Month 6 visits. Follicle-Stimulating Hormone (FSH) will be assessed at Month 3 FU at local laboratories for subjects who did not resume menses.

Blood samples will be analyzed by the central laboratory. Due to the COVID-19 situation, some samples may be collected by local laboratories.

Laboratory parameters values will be summarized for each visit for each treatment group and overall including within-group changes from baseline. In the event of repeated values, the last non-missing value per study day/time will be used.

Semi-quantitative laboratory results will be imputed as follows: "<X.X" will be imputed as "X.X/2" and ">X.X" will be imputed as "X.X".

Evaluation of shifts for changes from baseline to all visits, according to the normal ranges with categories "Low", "Normal", "High" where available (for ALT, AST, ALP, Bilirubin, Albumin, Calcium, Creatine Kinase) and according to normal/abnormal/abnormal clinically significant information collected otherwise, will be provided.

For Liver Function Test (LFT) parameters (ALT, AST, ALP, total bilirubin, albumin), evaluation of shifts for changes from baseline to the worst (highest) on-treatment value (including unscheduled assessments) according to the normal ranges with categories "Low", "Normal", "High" will be provided.

Assessments from local laboratories will not be included in summaries and shift tables, as normal ranges may not be comparable.

Sponsor:	ObsEva			
Protocol:	18-OBE2109-0	18-OBE2109-003		
Document Version No.:	V5.0	Document Date:	13-JUN-2022	

All laboratory data will be provided in data listings.

A subset listing will be presented for all abnormal clinically significant laboratory values.

For the lipid panel (Triglycerides, HDL, LDL, Total Cholesterol, LDL/HDL ratio), the percent change from baseline to each on-study visit will also be summarized.

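### Below-LOQ plasma concentrations are set to zero although geometric means are planned, so one such value makes that visit-by-group geometric mean zero or undefined

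*SAP*

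**What the plan says.** SAP 4.7 lists the summary statistics: "For descriptive statistics of plasma concentrations mean (arithmetic and geometric), standard deviation, median", followed by quartiles, extremes, CV% and the number of observations. The next sentence is the below-LOQ rule: "Concentrations below the limit of quantification (LOQ) will be assigned a value of zero". Protocol 13.5.6 puts the same rule beside the same statistics. The only other data-handling rule in SAP 4.7 concerns missing values, which are not imputed; it does not cover values below LOQ.

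The protocol synopsis sets the unit of summary: plasma concentrations "will be summarized by time point for each treatment group". SAP 3.1 limits the PK Set to "all subjects who received active study medication, had no major protocol deviations impacting PK evaluation and with available PK data", so placebo subjects do not contribute zeros. SAP 2.5.2 names two analytes, linzagolix and its metabolite KP017, and calls the PK analyses exploratory.

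SAP 4.2.9 decides which samples count. After Day 1, a sample is used if it was taken before the dose, or if no dose was taken that day, in which case it is treated as pre-dose. The timing condition is "PK assessment date is within +/-10 days of the theoretical visit and up to 2 days after last IMP intake for Month 6 visit". The limit on time since last intake applies to Month 6 only.

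**The concern.** A geometric mean needs positive values. The rule that turns below-LOQ values into zeros is written without exception, directly after a list of statistics that includes the geometric mean. The two instructions work together only while every sample in a cell is quantifiable.

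If a below-LOQ value occurs, the programmer has three options: print a zero, print nothing, or let the software treat the log of zero as missing. The third is the least visible. The table would show a geometric mean based on fewer subjects than the arithmetic mean and n beside it, with nothing to tell the reader. What is at stake is the accuracy of one descriptive statistic in the PK tables.

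**Working it through.** The documents state no figure on this point, so there is nothing to reproduce. Three checks follow.

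**1. Effect of one zero.** For n values, GM = (x₁·x₂·…·xₙ)^(1/n) = exp[(1/n)·Σ ln xᵢ]. If any xᵢ = 0, the product is 0 and GM = 0. In log form the sum contains ln 0, which is undefined. This holds whatever the other n − 1 values are.

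An illustrative lognormal sample (assumed: n = 150, median 1000 units, log-SD 0.6) shows how much depends on the unstated choice. With every value quantifiable, the geometric mean is 952.4 and the arithmetic mean 1092.3. For LOQ/2, the LOQ is assumed to lie between 1 and 50 units.

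| Values below LOQ | Arithmetic mean, zeros kept | GM, rule as written | GM, zeros left out (n used) | GM with LOQ/2 |
|---|---|---|---|---|
| 1 | 1084.1 | 0 | 950.7 (149) | 904 to 928 |
| 8 | 1027.5 | 0 | 943.4 (142) | 631 to 777 |

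The arithmetic mean moves little. The geometric mean depends on which convention is used, and the SAP names none that works.

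**2. Can a below-LOQ value arise?** Inputs: half-life of 15 to 20 h (Protocol 5.5.1) and the sample rules in SAP 4.2.9. The fraction remaining after h hours is 2^(−h/t½), assuming simple exponential decline:

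- 24 h: 33% to 44%
- 48 h: 11% to 19%
- 72 h: 4% to 8%
- 96 h: 1% to 4%

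A single missed dose (about 48 h since the last intake) leaves a sizeable level. Longer gaps leave little, and at Months 1 to 5 the SAP sets no limit on the gap. KP017 starts lower: Protocol 5.5.1 reports each plasma metabolite at under 10% of drug-related exposure. Below-LOQ values are therefore possible, and more so for KP017. Day 1 samples, taken at least 1.5 h after dosing, are less exposed.

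**3. How often would a cell be affected?** The documents give no below-LOQ rate p, so a range is assumed. The planned 150 subjects per group (SAP 4.1) is taken as the largest cell. With independent samples, P(at least one) = 1 − (1 − p)^n. For p = 1% and n = 150 this is 1 − 0.99^150 = 0.78. The second column assumes 130 usable samples.

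| Assumed p | n = 150 | n = 130 |
|---|---|---|
| 0.1% | 14% | 12% |
| 0.5% | 53% | 48% |
| 1% | 78% | 73% |
| 2% | 95% | 93% |

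The chance applies to one visit, one treatment group and one analyte.

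**The case against.** The strongest case against is that nothing in the documents shows a below-LOQ sample will occur. Several provisions make one less likely: the PK Set leaves out placebo subjects and major deviations affecting PK; Month 6 samples count only up to 2 days after the last intake; and withdrawal-visit sampling is not required without a dose the day before (Protocol 10.5 and 10.7.2). This stands as a limit on frequency. It does not remove the problem, because samples from days without a dose are kept and an isolated run of missed doses need not be a major deviation.

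It is also fair that little depends on this statistic. The arithmetic mean, median, quartiles and extremes remain computable with zeros, every concentration is listed with its dosing information, and PK modelling is a separate exercise. That sets the severity; it does not make the rule workable.

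A reader might infer three stronger points that the documents do not support.

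- Missed doses are bound to produce below-LOQ troughs. Without the LOQ, and with 11% to 19% of the level left at 48 h, this cannot be claimed.
- The PK summary as a whole cannot be computed. Only the geometric mean and any geometric CV are affected, and in product form the geometric mean is an uninformative zero.
- The SAP contradicts its own half-the-limit rule in 4.8.4. That rule ("Semi-quantitative laboratory results will be imputed as follows") is for clinical laboratory results and does not mention the PK assay. Different rules for different data are not an inconsistency.

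**Conclusion.** The point holds as a defect in a stated rule. Followed literally, SAP 4.7 and Protocol 13.5.6 give a zero or undefined geometric mean in any visit-by-treatment-group cell with one below-LOQ value. The arithmetic is certain. Whether and how often it applies is not, because the LOQ and the below-LOQ rate are not given. Over assumed rates of 0.1% to 2%, the chance per cell of up to 150 samples runs from 14% to 95%, and no single point in that span can be preferred on the documents. Severity is low: PK is exploratory and descriptive, and no efficacy or safety inference uses this statistic.

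**What to change.** Add one or two sentences to SAP 4.7, repeated as a footnote to the PK tables: zero is used for below-LOQ values in the arithmetic statistics; the geometric mean, and any geometric CV, is computed on quantifiable samples only; and the number of samples used and the number and percent below LOQ are reported for each visit, treatment group and analyte.

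The cost is a short SAP addition and two extra lines per table cell, with no new data. There is a small downside. With more than a few below-LOQ values, the geometric mean describes quantifiable samples only and is somewhat high: in the illustration with eight such values it is 943, against 631 to 777 under LOQ/2. The reported count makes this visible to the reader. LOQ/2 would also resolve the conflict, but its result depends on the LOQ, so the choice between the two is one of preference.
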